A blood sample will be obtained as part of the initial screening for hematology and serology (HIV, hepatitis B and C, and for HLA-B27 testing only for naïve subjects). Blood will be collected for hematology also on day 8 and 85 (visit 2 and 5 respectively). Each consented subject will have blood collected before vaccination on day 1 for baseline immunological testing and on day 8, 15, 29 and 85 (visit 2, 3, 4, and 5 respectively) post vaccination for immunological. Additional blood draw for preparation of standard serum will be done on day 29 post vaccination (visit 4). Urine pregnancy test will be done at visit 1 prior to vaccination and at visit 5. All individuals with neutropenia occurring at any time during the study will have additional blood draws to repeat complete blood count on a weekly basis until the neutropenia resolves. If neutropenia occurs at the last study visit, Complete Blood Count to be repeated on a regular basis until resolution (for classification of neutropenia during the trial, refer to [Section 5.4 Unscheduled Visits](#)).

Subjects will be observed at the clinic for 4 hour after vaccination on visit 1. Vital signs will be collected before vaccination and at 30 minutes and 4 hours post vaccination. Before leaving the clinic, they will be given a paper dairy card and trained to record in any adverse events occurring before visit 2 and will be reminded by phone call or email on day 3 and 7 post vaccination. These dairy cards will be collected and reviewed on day 8 post vaccination (visit 2).

Any unsolicited AE until visit 4, SAEs until study termination, all AEs leading to study withdrawal, reactive arthritis and severe neutropenia (AESI) and all concomitant medications associated with those events, will be collected and recorded in the subject's source document and in the eCRF. Further details on study procedure are found in [sections 5, Study Procedures and 7, Assessments](#).

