7.1.3 Evaluation of Adverse Events

Every effort should be made by the investigator to evaluate safety information reported by a subject for an underlying diagnosis and to capture this diagnosis as the event in the AE page. In other words, the practice of reporting only symptoms (e.g., “cough” or “ear pain”)

are better reported according to the underlying cause (e.g., “asthma exacerbation” or “otitis media”).

The severity of events reported on the Adverse Events CRF will be determined by the investigator as:

Mild: transient with no limitation in normal daily activity.

Moderate: some limitation in normal daily activity. Severe:
unable to perform normal daily activity.

The relationship of the study treatment to an AE will be determined by the investigator based on the following definitions:

1. Not Related

The AE is not related to an investigational vaccine if there is evidence that clearly indicates an alternative explanation. If the subject has not received the vaccine, the timing of the exposure to the vaccine and the onset of the AE are not reasonably related in time, or other facts, evidence or arguments exist that reasonably suggest an alternative explanation, then the AE is not related.

2. Possibly Related

The administration of the investigational vaccine and AE are considered reasonably related in time and the AE could be explained by exposure to the investigational vaccine or by other causes. 3. Probably Related

Exposure to the investigational vaccine and AE are reasonably related in time and no alternative explanation has been identified.

The relationship of the study treatment to an unsolicited AE will be determined by the investigator.

Note: solicited AEs will not be evaluated for relationship to study treatment. Grading for severity of solicited local and systemic AEs is described in [section 7.1.1, Solicited Adverse Events](#).

Adverse events will also be evaluated by the investigator for the co-existence of any of the other following conditions:

- “Medically attended adverse event”: an adverse event that leads to a visit to a healthcare provider.
- “New onset of chronic disease” (NOCD): an adverse event that represents a new diagnosis of a chronic medical condition that was not present or suspected in a subject prior to study enrolment.

- AEs leading to withdrawal: adverse events leading to study or vaccine withdrawal.

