7.1.4.1 Adverse Events of Special Interest

Adverse events of special interest (AESIs) are predefined adverse events that will be specifically highlighted to the investigator and will be summarized separately. Only AESI meeting the definition of SAE will be categorized and reported as such in this study.

Reactive arthritis (ReA) or Neutropenia will be collected and analyzed as an AESI for this study.

Reactive arthritis is defined as non-purulent joint inflammation that develops in response to an infection in another part of the body. Since the inflammation is triggered by a previous condition, it is termed “reactive”. Intestinal pathogens that have been associated with reactive arthritis include *Campylobacter*, *Salmonella*, *Yersinia*, *Clostridium difficile*, and *Shigella*. If reactive arthritis is caused by an auto immune response, there is at least a possibility that it could be initiated by vaccination of susceptible people with the 1790GAAH vaccine.

For diagnosis of ReA, imaging and aspiration are not required (unless clinically indicated).

Neutropenia is defined as decrease of neutrophil count asymptotically or symptomatically with ANC $<1.8 \times 10^9/L$, occurring at 7 days after vaccination. Its graded from grade 1 to 4 basing on neutrophil counts as follows: Grade 1 ANC $1.5- <1.8 \times 10^9/L$, Grade 2 ANC $<1.5 \times 10^9/L$, Grade 3 ANC $1.0- 0.5 \times 10^9/L$, and Grade 4 $<0.5 \times 10^9/L$.

This is completely diagnosed by laboratory testing for complete blood count.

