7.1.5 Methods for Recording Adverse Events and Serious Adverse Events

Findings regarding Adverse Events must be reported on an Adverse Events CRF, as specified in [section 7.1.1, Solicited Adverse Events](#), and on the VSAE form, if applicable, which is part of the Investigator Site File. All findings in subjects experiencing AEs must be reported also in the subject's source document.

All SAEs which occur during the course of the study, whether considered to be associated with the study vaccination or not and even if the information is incomplete, must be reported **within 24 hours of the site becoming aware of the event** to the Sponsor. Specific instructions and contact details for collecting and reporting SAEs will be provided to the investigator. Specifically, once an investigator becomes aware that a SAE has occurred in a study subject, the investigator (or designate) must complete a paper expedited Adverse Events report and forward it to the Sponsor **WITHIN 24 HOURS**. The report will always aimed to be completed as thoroughly as possible with all available details of the event and then dated and signed by the investigator (or designate). Even if the investigator does not have all information regarding a SAE, the report should still be completed and forwarded to the Sponsor within 24 hours. Once additional relevant information is received, the report should be updated and forwarded the Sponsor **WITHIN 24 HOURS**. The investigator will always provide an assessment of causality at the time of the initial report.

All SAEs are also to be documented on the Adverse Events CRF. Any medication or other therapeutic measures used to treat the AE will be recorded on the appropriate CRF(s) in addition to the outcome of the AE.

Only AESI meeting the definition of SAE will be categorized and reported as serious in this study by the investigator within 24 hours. However all other AESI irrespective of their grading will be recorded in the adverse event page of eCRF and the source documents.

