7.1.7 Safety Laboratory Measurements

For list of safety laboratory measurement, refer to synopsis [Table 2, Hematological Safety](#) [Table 3](#).

Safety laboratory measurement will be performed as described in [Section 3.5, Collection of Clinical Specimens](#).

Significant alterations in hematology will be clinically assessed by the investigator's medical judgment based on interpretation of deviations from institution's normal values.

Any abnormality in laboratory measurements classified as clinically significant must be reported in the Adverse Event CRF form.

If a subject is to have blood drawn testing for safety laboratory for repeat safety assessment (i.e., in case of markedly abnormal safety laboratory parameter), investigator's medical judgment will be applied concerning values that would trigger reanalysis and frequency of repeats. If neutropenia is observed at a visit, a complete blood count will be repeated on a weekly basis until resolution.

Safety laboratory assessments will be performed at the site laboratory, and results of these tests will be recorded in the source documents and in the CRF.

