6.5.2.5. Clinical Safety Laboratory Investigations

The investigator must assess all safety laboratory results (see **section 7.1.7** of the study protocol). Clinically significant modifications in hematology test values will be assessed by medical judgment based on interpretation of deviations from the institution's normal values.

All laboratory safety data will be analyzed descriptively by study group. Safety laboratory data will be shown in a 3 x 3 table by visit using categorization of laboratory according to institutional normal reference range (below, within, above).

The frequencies of subjects with clinical laboratory values below, within, or above normal ranges and change-from-baseline values will be tabulated for each clinical laboratory variable by vaccine-group and time-point of assessment (3 x 3 shift tables).

Laboratory values that are outside the normal range will also be flagged in the data listings, along with corresponding normal ranges and assessment of clinical significance.

For subjects presenting at least one clinically significant value, an additional listing will be provided of all laboratory results by vaccine group, by subject, and by relevant parameter. Clinical significance assessed by the investigator will be presented.

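### Neutropenia as an AESI is defined inconsistently in severity and timing, its ANC grades overlap, and no SAP table shows its depth

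*Protocol*

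**What the plan says.** All protocol references are to Version 2.

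- **Severity.** Section 3.1 lists among the events to be recorded "all AEs leading to study withdrawal, reactive arthritis and severe neutropenia (AESI) and all concomitant medications associated with those events". Section 7.1.4.1 has no such limit: "Reactive arthritis (ReA) or Neutropenia will be collected and analyzed as an AESI for this study". The synopsis and SAP Section 2 are also unqualified.
- **Threshold and timing.** Section 7.1.4.1 states: "Neutropenia is defined as decrease of neutrophil count asymptotically or symptomatically with ANC" below 1.8 × 10⁹/L (the adverb evidently means asymptomatically). The same sentence places the event at 7 days after vaccination. Sections 3.1 and 5.4 order repeat counts for neutropenia at any time in the study and deal separately with onset at the last visit.
- **Grades.** Section 7.1.4.1 continues "Its graded from grade 1 to 4 basing on neutrophil counts as follows": Grade 1 from 1.5 to below 1.8, Grade 2 below 1.5, Grade 3 from 1.0 to 0.5, Grade 4 below 0.5.
- **AE severity.** Section 7.1.3 rates AE CRF severity by daily activity, for example "Mild: transient with no limitation in normal daily activity". It has no laboratory criterion.
- **Recording.** Section 7.1.5, after dealing with serious AESIs: "However all other AESI irrespective of their grading will be recorded in the adverse event page of eCRF and the source documents". Section 7.1.7: "Any abnormality in laboratory measurements classified as clinically significant must be reported in the Adverse Event CRF form".
- **Analysis.** SAP 6.5.2.3 summarises AESIs among the unsolicited AEs. SAP 6.5.2.5: "Safety laboratory data will be shown in a 3 x 3 table by visit using categorization of laboratory according to institutional normal reference range". It also plans listings that flag out-of-range values.

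**The concern.** Neutropenia is one of two named AESIs, and the trial has no data monitoring committee (3.7) and no stopping rule (3.6), so the final AESI and laboratory summaries carry the evidence on it. Haematology is drawn from every subject at Day 8 and Day 85. The count itself is therefore objective; what varies is whether it is labelled an AESI, which grade it receives, and whether any table shows how low it was.

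Two things are at stake. First, the AESI count could depend on which section the site or the programmer follows. Secondly, a deep and a shallow fall could look the same in every summary table: the AE severity scale does not use the ANC, the ANC scale gives two answers at low values, and the SAP uses neither the 1.8 threshold nor the grades.

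**Working it through.** The plan gives no figure to reproduce; Section 8.5 makes no sample-size calculation. The check applies the printed rules to test values.

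**1. Grades.** For an ANC of x (× 10⁹/L), the bands as printed are G1: 1.5 ≤ x < 1.8; G2: x < 1.5; G3: 0.5 ≤ x ≤ 1.0; G4: x < 0.5.

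| ANC | Grades met | Below 1.8? |
|---|---|---|
| 0.4 | 2 and 4 | yes |
| 0.5, 0.7, 1.0 | 2 and 3 | yes |
| 1.2 | 2 | yes |
| 1.5 to 1.79 | 1 | yes |
| 1.8 | none | no |

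Every value of 1.0 or below meets two grades. Every value above 1.0 and below 1.8 meets exactly one.

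**2. AE severity.** A transient, symptom-free low count limits no activity, so it fits mild under 7.1.3 whether the ANC is 1.7 or 0.4. No section links that scale to the ANC grades.

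**3. A Day 8 case.** Sections 3.1 and 7.1 collect every unsolicited AE to Visit 4, and 7.1.5 records AESIs whatever their grade. The event should be on the AE CRF.

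**4. A Day 85 case.** Take an ANC of 1.2, symptom-free, not serious, not judged clinically significant, not medically attended. Under 7.1, general AE collection has ended at Visit 4; Table 2 and Section 5.5 add only new chronic disease and AEs leading to withdrawal. The event reaches the AE CRF only if it is an AESI:

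- Synopsis and SAP Section 2: yes. Neutropenia is unqualified and AESIs run to Visit 5.
- Section 3.1: only if severe, a term it does not define. On the 7.1.3 scale it is not severe.
- Section 7.1.4.1: the threshold is met, but the 7-day timing is not.
- Sections 3.1 and 5.4 on repeat counts: treated as neutropenia at the last visit, with follow-up counts.

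The texts give different answers for the same value.

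**5. What the SAP shows.** Let L be the institutional lower limit, which the documents do not state. A count x falls in the below category if x < L.

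- L = 1.5 (assumed): counts of 1.5 to below 1.8 show as within range.
- L = 1.7 (assumed): counts of 1.7 to below 1.8 show as within range.
- L of 1.8 or higher: no count under 1.8 shows as within range.
- For any L above 1.7, counts of 0.4 and 1.7 share the same cell.

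Exclusion criterion 24 bars a screening ANC below 1.8, so any later count under 1.8 in an eligible subject is a fall since screening.

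**6. Size.** Assume all 50 subjects are evaluable and use the SAP's Clopper-Pearson interval.

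- One case counted: 1/50 = 2.0%. Lower limit = Beta(0.025; 1, 50) = 0.05%; upper limit = Beta(0.975; 2, 49) = 10.6%.
- The same case not counted: 0/50. Upper limit = 1 − 0.025^(1/50) = 7.1%.

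**The case against.** The strongest reply is that the capture rules work when read together. Section 3.1 sends the reader to 5.4 for classification, and 5.4 points to 7.1.4.1. Section 7.1.5 overrides any grade restriction on recording. Section 7.1.7 adds a floor for clinically significant laboratory findings; it does not compete with the AESI rule. Weekly counts follow any neutropenia during the study. The SAP itself names neutropenia without a qualifier, and with at most 50 subjects a listing that flags each out-of-range count shows its depth. No section says that severe in 3.1 means severe on the 7.1.3 scale.

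Most of this stands. A reader might infer that a symptom-free ANC of 0.4 at Day 8 would be missed altogether. The documents do not support that: it falls in the unsolicited AE window, is an AESI under 7.1.4.1, and would be listed. Nor do the overlapping grades produce the mild label, which comes from the separate 7.1.3 scale. Nor is the ANC scale unusable: it is unambiguous above 1.0.

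The reply does not cover Day 85. There the AESI label decides whether the case in step 4 is collected as an AE, and following 3.1 to 7.1.4.1 leads to the 7-day timing. The secondary endpoint counts unsolicited AEs over 84 days, but Section 7.1 and Table 2 do not collect all AEs at Visit 5, so it does not close the gap. The listings flag by institutional range, so they do not flag a count under 1.8 that lies within that range, and they are not summaries by group.

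**Conclusion.** The inconsistency is real and should be corrected. The AESI wording conflicts on severity and on timing, and every ANC of 1.0 or below carries two grades. Capture is not in serious doubt at Day 8; what is lost there is depth in the summary tables. At Day 85, capture on the AE CRF depends on wording that conflicts. In a trial of this size, one such decision determines whether a named risk appears in the AESI table at all (1/50 or 0/50).

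The grade overlap, the conflicting definitions and the absence of an ANC-grade table follow from the text alone. The shift-table point depends on the unstated institutional limit and disappears if that limit is 1.8 or higher, although depth is still not shown. The one-case illustration assumes 50 evaluable subjects and predicts no event rate. All analyses are descriptive, so no formal inference is affected.

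**What to change.** 1. Reconcile Protocol Sections 3.1, 5.4, 7.1.4.1 and 7.1.5, with the synopsis and SAP Section 2, to one AESI definition of neutropenia that covers both severity and timing. Which definition is right is for the sponsor. Copying 7.1.4.1 into 3.1 as it stands would not be enough, because it would carry the 7-day timing into a section that also provides for neutropenia at any time.
2. Have the sponsor reconcile the four ANC bands so that each value has exactly one grade.
3. In SAP 6.5.2.5, add a table by Shigella, Pla+Naïve and Total of each subject's worst post-vaccination ANC by reconciled grade. Derive it from laboratory data, scheduled and unscheduled, with Day 8 and Day 85 included. Section 5.5.1 keeps results obtained after study termination out of the eCRF, so the table would stop at termination, and a footnote should say so.
4. For neutropenia AEs, report the ANC grade alongside the activity-based severity.

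The cost is protocol wording and one extra table from data already collected. The reported neutropenia count may be higher as a result.

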3.2 Study Period

Each subject should expect to participate in the study for 85 days, from the time of enrolment through the last study visit.

3.3 Blinding Procedures

No blinding procedures will be applied for this study.

3.4 Data Collection

3.4.1 Data Collected from Subjects

The following data will be collected from each subject over the duration of their study participation:

- Demographic Information

- Medical History
- Post-vaccination immediate reactions
- Vital signs including but not limited to body temperature
- Adverse Events
- Concomitant Medications

All data collected must only be identified using the GSK Subject ID and Subject code, as described in [section 5.1.4, Randomization](#).

3.4.2 Tools Used for Data Collection

Subject Diary

Paper Diaries, hereafter referred to as Subject Diaries will be the only source document allowed for solicited local and systemic adverse events (including body temperature measurements), starting approximately 6 hours post-vaccination and collected by the subject. The following additional rules apply to documentation of safety information collected in the Subject Diary.

The Investigator or delegated staff should monitor the Subject's Diary status throughout the study for compliance and any solicited local and systemic adverse events that were of concern to the subject.

1. No corrections or additions to the information recorded by the subject within the Subject Diary will be allowed after it is delivered to the site.
2. Any blank or illegible fields on the Subject Diary must be described as missing in the CRF.

Case Report Forms

An electronic data capture (EDC) system (e.g., Inform™) will be used to expedite the entry of data. A qualified site staff member(s) will enter data in English into the web enable EDC system in a timely manner; the data will be stored in GSK clinical database management system. eCRF data will be reviewed routinely by GSK Data Management (DM) Group and GSK clinical monitors or representatives.

The information from the diary will be entered in the eCRF at visit 2. All data not recorded directly on the eCRFs must be verified by checking eCRF entries against source documents in order to ensure that the data have been completely and accurately reported as required by the study protocol.

Source data verification will be performed and recorded following GSK internal SOP. The subject must also allow access to his/her medical records. Each subject will be informed of this prior to the start of the study.

The following additional rules apply to documentation of Subject Diary information collected in the CRFs:

1. The site must enter all readable entries from the Subject Diary into the eCRF, including those values that may be biologically implausible (e.g. body temperature: 400°C).
2. Any illegible or implausible data should be reviewed with the subject. If an underlying solicited or unsolicited adverse event is described on review with the subject, this should be described in the source document and reported as an unsolicited adverse event in the Adverse Event CRF (e.g., if the subject above confirms body temperature of 40°C on the day in which body temperature: 400°C was written into his/her Subject Diary, this fever of 40°C should be recorded in the Adverse Event CRF).
3. Any newly described safety information (including a solicited adverse event) must not be written into the Subject Diary and must be described in the study file (studyspecific workbook) as a verbally reported adverse event. Any adverse event reported in this fashion must be described as an unsolicited adverse event and therefore entered on the Adverse Event CRF.

3.5 Collection of Clinical Specimens

Collected samples will be used for protocol mandated research and purposes related to the improvement, development and quality assurance of the laboratory tests described in this protocol. This may include the management of the quality of these tests, the maintenance or improvement of these tests, the development of new test methods, as well as making sure that new tests are comparable to previous methods and work reliably.

It is also possible that future findings may make it desirable to use the samples acquired in this study for future research, not described in this protocol. Therefore, all subjects in countries where this is allowed/all subjects will be asked to give a specific consent to allow the Sponsor or a contracted partner to use the samples for future research. Future research will be subject to the laws and regulations in France and will only be performed once an independent Ethics Committee or Review Board has approved this research. Information on further investigations and their rationale can be obtained from GSK.

Any sample testing will be done in line with the consent of the individual subject. If additional testing is performed, the marker priority ranking given in the table below may be changed.

Table 4 Blood For Immunological purposes

Blood sampling timepoint		Subset /Subcohort Name	No. subjects	Component	Components priority	rank
Type of contact and timepoint	Sampling timepoint	All subjects	50	HIV*	NA	
		All subjects	50	anti-HBsAg*		
		All subjects	50	Hepatitis C*		

		Naïve subjects	26	HLA-B27	
Visit 1 (Day 1)	Pre-Vacc		50	Anti LPS IgG ELISA	NA
Visit 2 (Day 8)	Post-Vacc 1		50	Anti LPS IgG ELISA	NA
Visit 3 (Day 15)	Post-Vacc 2		50	Anti LPS IgG	NA
Visit 4 (Day 29)	Post-Vacc 3		50	Anti LPS IgG	1
	Standard Serum		50	Standard pool for ELISA	2
Visit 5 (Day 85)	Post-Vacc 4		50	Anti LPS IgG	NA

* The results of this testing might potentially impact the subject medical care

Processing of each specimen should be completed by a qualified site member and in accordance with the study-specific laboratory manual. Testing of clinical specimens will be performed by GSK Clinical Laboratory Science (CLS), Marburg, (Germany) or a delegated laboratory. Refer to the study-specific laboratory manual for additional details.

Blood Specimens

Approximately 15 mL blood draw will be obtained for hematological and serological (HIV, hepatitis B and C for subjects who were in the parent study. Naïve subjects will however have 25mL of blood drawn for HLA-B27 testing in addition of the hematological and serological (HIV, hepatitis B and C) tests as part of the initial screening. One additional blood draw of 6 mL for hematological tests will be obtained at 8 days (Visit 2) and 85 days (Visit 5) after vaccination (see [Table 2](#)). Each subject will have 20 mL of blood drawn for immunological studies before vaccination at Day 1 and 8, 15, 29 and 85 days after vaccination. For the purpose of creating a standard reference serum for the serological assay, study subjects will provide an additional blood sample of 20 ml at 29 days after vaccination.

All individuals with neutropenia occurring at any time during the study will have additional 6mL blood draws to repeat complete blood count on a weekly basis until the neutropenia resolves.

Clinically significant modifications in hematology will be assessed by medical judgment based on interpretation of deviations from institution's normal values and recommendations from [CBER FDA GUIDANCE FOR INDUSTRY: Toxicity Grading Scale for Healthy Adult and Adolescent Volunteers Enrolled in Preventive Vaccine Clinical Trials](#).

The total amount of blood collected over the study period per subject will be approximately 157 mL including screening for HLA for a subject who was not part of the parent study and the additional blood sample at day 29 for the standard pool serum for immunogenicity and excluding possible repeats of hematological tests in case of neutropenia.

Serum samples will be stored frozen below -20°C. The sera aliquots will be shipped according to guidelines provided by GSK to the laboratories for analysis. The serologic assays will be conducted at the GSK Clinical Laboratory Science, Marburg, (Germany) or a delegated laboratory.

Aliquots of sera will be archived for 20 years at the GSK laboratory in Marburg (Germany) for future research on immunogenicity of the *Shigella* vaccines. Study-related future research may include additional evaluation of immunogenicity on *Shigella sonnei* (i.e. IgM, IgA against the O antigen or IgG against other antigens of *Shigella sonnei*). It may not be possible to contact individual participants in the future in order to disseminate results obtained from research conducted on archived samples. However, these results, if relevant, will be published in peer-reviewed journals and disseminated to the scientific community. An archival time of 20 years should cover the entire vaccine development time, including the possibility to address potential questions from regulators during the registration time.

Complete instructions for processing, labeling, storage and shipping of samples are included in the Clinical Specimen Laboratory Manual provided to the investigators and available in the Investigator Site File.

Blood samples must be collected in the appropriate manner, using exclusively materials and guidelines supplied by GSK. The investigator must ensure that his/her personnel and the laboratory(ies) under his/her supervision comply with this requirement. The results of safety testing will be recorded in the source document and eCRF.

Urine Specimens

In this study urine samples will be collected from women of childbearing potential only for pregnancy testing before vaccination at Day 1 (visit1) and at study termination (visit 5).

